### 9.4 Study visits

The procedures to be included in each visit are documented in the schedule of procedures tables (Section 4). Each visit is assigned a time-point and a window period, within which the visit should be conducted. Whether a visit can occur out of window will be decided on a case-by-case basis by the study investigators.

### 9.4.1 Vaccination Visits

Vaccination visits are held at the study site. The visit procedure for the vaccination visits, for both cohort 1 and cohort 2, will be as follows:

- Ensure that participant consent remains valid and verbally confirm continued consent
- Obtain and document interim medical history since the screening visit including medication
  use and other vaccinations, and check eligibility criteria, specifically temporary exclusion to
  vaccination, and perform a targeted physical examination (if required to reassess eligibility)
- Record temperature, pulse and blood pressure
- Perform highly sensitive urinary pregnancy test for females of childbearing potential (section 8.4); alternatively
- Perform blood draw (as per section 9.6)
- Administer vaccine or placebo by IM injection into the deltoid muscle (ideally the nondominant arm)

RECRef: 23/SC/0268 NIV001: A study of a new vaccine against Nipah Page 35 of 71 IRAS project ID: 1007433 Virus in adults aged 18 to 55

- Post-vaccination observation of volunteer for a minimum of 30 minutes following vaccine administration
- On the first vaccination visit (D0), participant is provided access and training to use the electronic diary (eDiary) using the participant's personal email address for the set-up
- Schedule next visit and re-iterate participant requirements such as completion of the eDiary entries
- On the subsequent vaccination visit, review of AEs and SAEs since the last visit

### 9.4.2 Follow-Up Visits

Follow-up visits are held at the study site (or remotely, if required, see section 9.4.4). Follow-up visits may require the following procedures:

- Review of concomitant medications and other vaccinations since the last visit
- Review of AEs/AESIs/SAEs, as appropriate, since the last visit
- Review eDiary entries and laboratory blood tests
- Record oral temperature, pulse and blood pressure
- Perform blood draw (as per section 9.6)
- Schedule next visit and re-iterate participant requirements such as eDiary entries

### 9.4.3 Unscheduled Visits

Additional visits or procedures may be performed at the discretion of investigators, for example for further medical history and physical examination, additional blood tests or other investigations if clinically relevant.

#### 9.4.4 Missed Visits

In exceptional circumstances, where follow-up visits would otherwise be missed entirely, visits may alternatively be conducted remotely via phone or video calling. This will allow a minimum set of safety and adverse event data to be collected.

### 9.5 Electronic Diary (eDiary)

Following each vaccination, participants will have access to an eDiary system (using their personal email address) to allow them to self-report solicited and unsolicited AEs. Each participant will be given unique log-in details associated with their study number. Training for this will be given at the first vaccination visit. A paper copy of the diary may be provided to allow for completion in the event of inability to access the online version for any reason. Local site (blinded) clinical teams will have access to the eDiary in order to review data inputted by participants, and the system automatically sends an email to investigators if a grade 3 AE has been inputted by a participant. The study team will be following up on compliance and will contact participants via phone, text or email to remind participants to fill in the eDiary if this is not being done. The electronic system also automatically sends a reminder to the participant if the eDiary hasn't been completed for the previous 24-hour period.

RECRef: 23/SC/0268 NIV001: A study of a new vaccine against Nipah Page 36 of 71 IRAS project ID: 1007433 Virus in adults aged 18 to 55

# 9.6 Participant Samples

#### 9.6.1 Clinical Laboratory Samples

Blood will be drawn (at different time points according to the schedule of procedures, section 4) for the following laboratory tests. The processing and analysis of the blood will be carried out at an accredited local clinical laboratory.

- Haematology:
  - Full Blood Count (Including: Haemoglobin, platelet count, total white cell count, neutrophil count, lymphocyte count, eosinophil count)
- Biochemistry:
  - Urea and Electrolytes (Including: Sodium, Potassium, Urea and Creatinine)
  - Liver Function Tests (Including: ALT, ALP, Bilirubin, Albumin)
- Diagnostic serology (screening only):
  - Screening tests for Hepatitis B, Hepatitis C and HIV infection (Including: HBsAg, HCV antibodies, HIV antibodies)
- Immunology (first visit only):
  - o Human Leukocyte Antigen (HLA) typing

Additional safety blood tests may be performed if clinically relevant at the discretion of the medically qualified investigator(s).

# 9.6.2 Immunology Samples

# 9.6.2.1 University of Oxford Research Laboratories

Immunogenicity will be assessed by a variety of immunological assays. As the secondary objective, NipahB glycoprotein G-specific serological response will be measured by ELISA. Exploratory objectives include NipahB neutralising antibody responses measured by live or pseudo neutralising assays, NipahB glycoprotein G T cell response measured by IFN-g ELISPOT, and cellular immune responses to Nipah virus measured by ICS, proliferation and/or whole blood assays.

Other exploratory immunological assays may include changes in anti-PF4 antibodies levels, cytokine analysis and other antibody assays, production of monoclonal antibodies, DNA analysis of genetic polymorphisms potentially relevant to vaccine immunogenicity, and gene expression studies, amongst others.

#### 9.6.2.2 Other Research Laboratories

Collaboration with other specialist laboratories in the UK, including laboratories at the trial site(s), Europe and outside of Europe for further exploratory immunological tests may occur. This would involve the transfer of serum, plasma and peripheral blood mononuclear cells (PBMCs) to these laboratories, but these samples would remain de-identified. Informed consent for this will be gained from the participants. Immunological assays will be conducted according to local SOPs.

#### 9.6.3 Urine Samples

For female volunteers of childbearing potential only, urine will be tested for human chorionic gonadotrophin (hCG) at screening and immediately prior to each vaccination. Alternatively, hCG blood sampling may be used instead.

RECRef: 23/SC/0268 NIV001: A study of a new vaccine against Nipah Page 37 of 71

# 9.6.4 Retention of Samples

Participants will be informed that they may opt-in to the Oxford Vaccine Centre Biobank study (REC 21/SC/0161) to allow long-term storage of biological samples collected under the NIV001 protocol for use in possible future research. The OVC Biobank study is covered by a separate study protocol and consent process. Participants will be informed that declining to take part in the OVC Biobank study will not affect their participation in this study. If a participant elects to decline to take part in the OVC Biobank, all of their remaining samples will be destroyed after the required period of storage to meet Good Clinical Practice (GCP) and regulatory requirements.

# 9.7 Discontinuation/Withdrawal of Volunteers

Each participant can exercise their right to withdraw from the study at any time without giving a reason. In addition to consent being withdrawn by a participant, the investigator may discontinue a participant from the study at any time for the following, although not exhaustive, reasons:

- The investigator considers it necessary for participant safety
- Significant non-compliance with study requirements
- The participant is lost to follow up

In circumstances pertaining to the safety of the participant, the DSMC chair, DSMC committee or Investigator may choose to discontinue further vaccination and/or specific study procedures for an individual participant. However, participants should otherwise continue to attend the follow up visit schedule and follow up procedures unless they withdraw consent for this. Such circumstances may include the following non-exhaustive reasons:

- Pregnancy (further details on management of participants who become pregnant are provided in section 8.4)
- An adverse event which requires discontinuation of the study vaccinations or results in an inability to continue to comply with study procedures
- Ineligibility (either arising during the study or in the form of new information not declared or detected at screening)

Withdrawal from the study will not result in exclusion of existing data generated by the participant from analysis. Participants can request that their samples are destroyed at any point during or after the study (although data that has already been generated from samples that have been analysed up to that point will be retained). The reason for withdrawal, if given, will be recorded in the eCRF. Participants who withdraw from the trial after randomisation but prior to receipt of their first vaccine dose may be replaced by a further volunteer who will undergo separate randomisation.

# 9.8 Special Circumstances: COVID-19

#### 9.8.1 Study Conduct/Risk Assessment

It is difficult to predict the time course of the COVID-19 pandemic. At all times the safety and welfare of study participants remains paramount.

On the basis of the COVID-19 situation, the Chief Investigator may perform a risk assessment as necessary and this may involve discussion with relevant parties (such as the DSMC and Regulatory Authorities), to determine:

RECRef: 23/SC/0268 NIV001: A study of a new vaccine against Nipah Page 38 of 71

- Appropriateness to initiate vaccinations
- Appropriateness to continue the trial once started
- Necessity to extend trial duration

Dependant on the prevailing COVID-19 situation, the conduct of the trial may be modified in the interests of participant safety. Such measures may include but are not limited to:

- Pausing further vaccinations
- Modifying study visits and procedures, for example, study visits could be conducted by phone or video calling where appropriate

#### 9.8.2 COVID-19 Infection Control Measures at Visits

Infection control procedures including the safe handling of clinic visits, a COVID-19 secure workplace, and maintaining staff safety will be included in study site SOPs. These will be updated as appropriate in line with NHS/UK Government policies.

# 9.8.3 Participants Isolating

Should a participant be isolating due to an intercurrent illness including COVID-19, and are thus unable to attend a particular scheduled visit(s), a telephone/video consultation may be arranged in order to obtain follow-up safety information, and the visit may be re-scheduled, depending on the timelines.

#### 9.8.4 Participants with Intercurrent Illness Symptoms

Participants who develop intercurrent illness symptoms, including those of COVID-19 with or without test confirmation, must wait to receive a trial vaccine until they feel they have fully recovered. The decision to proceed with subsequent trial vaccinations will be at the discretion of the Investigators, and each individual will be evaluated by a study doctor before proceeding (including physical examination). The trial clinician must deem that the participant has fully recovered and have no symptoms from their illness.

# 9.8.5 Participants Invited For COVID-19 Vaccination During the Trial

Participants who become eligible for a COVID-19 vaccination will be invited to discuss this with the study team. If agreed by the participant, the trial team will identify a mutually agreeable time to receive a COVID-19 vaccine. If a vaccination offer coincides with a planned trial vaccine, the trial vaccine will be rescheduled to at least 14 days before or after the COVID-19 vaccine, within the allowable visit windows. This is in line with the UK Green Book COVID-19 vaccination recommendations for other vaccines which recommends an interval of "at least 7 days". Participants will not be impeded in taking up an offer of a COVID-19 vaccine. If a participant receives a COVID-19 vaccine during the trial, both the vaccine and date of administration will be requested and recorded in the eCRF.

If the participant receives an adenoviral-based COVID-19 vaccine (or any other adenoviral vaccine) during the trial, the participant will no longer be eligible to continue with the trial.

RECRef: 23/SC/0268 NIV001: A study of a new vaccine against Nipah Page 39 of 71 IRAS project ID: 1007433 Virus in adults aged 18 to 55

Virus in adults aged 18 to 55 Protocol V4.0, 16 AUG 2024

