### **6 OBJECTIVES AND ENDPOINTS**

# 6.1 Objectives, Outcome Measures and Evaluation Timepoints

Outcome	Objective	Outcome measure	Evaluation timepoints 
Primary	To assess the safety and tolerability of ChAdOx1 NipahB in healthy volunteers aged 18-55	a) Occurrence of solicited local reactogenicity signs and symptoms b) Occurrence of solicited systemic reactogenicity signs and symptoms c) Occurrence of unsolicited adverse events (AEs) d) Occurrence of abnormal safety laboratory measures	7 days following each vaccination
		e) Occurrence of serious adverse events (SAEs) and adverse events of special interest (AESIs)	Cohort 2 : D0, D1, D14, D28, V2, V2+1, V2+14, V2+28 Duration of the study (D0 to V2+281)
Secondary	To assess the immunogenicity of ChAdOx1 NipahB vaccine in healthy adult volunteers aged 18-55	NipahB glycoprotein G-specific serological response as measured by ELISA	Cohort 1: D0, D14, D28, D56, V2, V2+14, V2+28, V2+56, V2+281 Cohort 2: D0, D14, D28, V2, V2+14, V2+28, V2+281
Exploratory 	Immunological profiling	a) NipahB neutralising antibody responses measured by live or pseudoneutralisation assays b) NipahB glycoprotein G T cell response measured by IFN-g ELISPOT c) Cellular immune response to Nipah virus measured by ICS, proliferation and/or whole blood assays	Timepoints will be detailed in the laboratory analysis plan
	To assess anti-PF4 antibody levels following vaccination	Change in anti-PF4 antibody level measured by ELISA	D0, D14, V2+14
	To assess anti-vector immunity following vaccination	Binding and/or neutralising antibody responses against ChAdOx1	Timepoints will be detailed in the laboratory analysis plan

Visit and procedure timepoint windows are defined in section 4 (Schedule of Procedures). These exploratory endpoints may be performed; additionally, sample analysis for the completion of exploratory endpoints may be performed under the ethically-approved Oxford Vaccine Centre (OVC) Biobank protocol (REC 21/SC/0161). Further exploratory assays/analyses may be carried out (see section 9.6.2).

RECRef: 23/SC/0268 NIV001: A study of a new vaccine against Nipah Page 26 of 71

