#### 8.2 Temporary Exclusion Criteria

The following applies to both vaccination visits. If the temporary exclusion resolves within the time constraints of the trial visits, the participant can be enrolled and/or progression in the trial can continue.

- 1. Receipt of any systemic corticosteroid (or equivalent) treatment within 14 days prior to vaccination, or for more than 7 days consecutively within the previous 3 months.
- 2. Febrile illness (oral temperature ≥37.5°C) or systemically unwell on the day of vaccination.
- 3. Receipt of systemic antibiotics will result in vaccination being postponed until 7 days after the last antibiotic dose. This does not apply to topical antibiotic preparations.
- 4. Use of antipyretics in the 4 hours prior to vaccination.
- 5. Occurrence of a laboratory adverse event, which in the opinion of the Investigator, requires further time and/or investigation to resolve or stabilise prior to a dose of vaccine being administered.
- Occurrence of any illness or adverse event, which in the opinion of the Investigator, requires of further time and/or investigation to resolve or stabilise prior to a dose of vaccine being administered.
- 7. Receipt of other vaccines. These must be administered 30 days before or after study vaccines EXCEPT influenza and COVID-19 vaccines which may be given 14 days before or after study vaccines. Receipt of an adenoviral-vectored vaccine would preclude the participant from further trial vaccinations (see Exclusion Criteria 2).
- 8. Any other significant disease, disorder or finding which may significantly increase the risk to the volunteer if included in the study, affect the ability of the volunteer to participate in the study, or impair interpretation of the study data.

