#### 10.7 Concomitant Medication

The use of all concomitant medication prescribed or over-the-counter, will be recorded in the eCRF. Concomitant medication that will result in temporary exclusion or withdrawal of volunteers from further vaccination are detailed in section 8.2. There is otherwise no restriction on the use of concomitant medication.

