# 11.15 Reporting Procedures for SAEs

SAEs will be collected throughout the entire trial period (from first vaccination to the final study visit or withdrawal).

All SAEs will be reported on the SAE form (paper or electronic) to the CI (as delegated by the Sponsor) immediately (or within 24 hours at the latest) of the site study team becoming aware of the event being defined as serious. Causality of SAEs will be assessed by the blinded investigator.

The CI on behalf of the Sponsor will be responsible for unblinding in the event of serious adverse reactions and will be responsible for the reporting of any SUSARs (as detailed in section 11.17). Any SUSAR must be reported to the DSMC.

Unrelated SAEs will be reported to the DSMC for discussion at the next scheduled DSMC review (11.22.1).

RECRef: 23/SC/0268 NIV001: A study of a new vaccine against Nipah Page 47 of 71

Additional information received for a case (follow-up or corrections to the original case) needs to be detailed on a new SAE form notified by the study team to the CI, who will then notify the DSMC.

The DSMC will perform an independent review of SAEs and request any further information required in a manner adherent to the procedures and timelines of the DSMC Charter. Documentation of this review will be kept in the TMF.

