# 13.1.4 Criteria For Termination of the Trial

The CI and DSMC will have the right to terminate the study at any time on grounds of participant safety. If the study is prematurely terminated the Investigator will promptly inform the participants and will ensure appropriate therapy and follow-up. If the study is halted, the MHRA and relevant Ethics Committee will be notified within 15 days of this occurring.

RECRef: 23/SC/0268 NIV001: A study of a new vaccine against Nipah Page 54 of 71

In the event of the trial being terminated early, follow-up of enrolled participants will still continue as planned for safety reasons, with the exception that further vaccination will not be given and study procedures will be modified to monitor safety only.

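### Section 9.8.5 ends a participant's eligibility for the whole trial after an outside adenoviral vaccine, where section 8.2 bars only further dosing and other sections keep safety follow-up going

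*Protocol*

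**What the plan says.** Section 9.8.5 deals with COVID-19 vaccination during the trial. Its last sentence covers an adenoviral-based COVID-19 vaccine or any other adenoviral vaccine, and concludes that "the participant will no longer be eligible to continue with the trial". It sets no time limit and makes no exception for people who have had both injections.

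Section 8.2 item 7 covers the same event: "Receipt of an adenoviral-vectored vaccine would preclude the participant from further trial vaccinations". It does not mention follow-up. Section 10.7 describes the effect of section 8.2 in the same terms: "Concomitant medication that will result in temporary exclusion or withdrawal of volunteers from further vaccination are detailed in section 8.2".

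Section 9.7 lists ineligibility that arises during the study among the circumstances in which vaccination or specific procedures may be stopped, and adds that "participants should otherwise continue to attend the follow up visit schedule and follow up procedures unless they withdraw consent for this". Section 8.3 keeps a participant in follow-up after a serious adverse reaction or a pregnancy. Sections 11.24.1 and 11.24.2 each say that everyone vaccinated is followed for safety to the planned end of participation, subject to consent. If the whole trial is stopped early, section 13.1.4 says "follow-up of enrolled participants will still continue as planned for safety reasons, with the exception that further vaccination will not be given".

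Section 6.1 sets the period for primary outcome (e), SAEs and AESIs, as D0 to V2+281. Under section 11.15, SAE collection starts at the first vaccination and stops at the last visit or when the participant withdraws.

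**The concern.** One event has two differently worded consequences. Section 8.2 stops dosing, while section 9.8.5 ends eligibility for the trial. Elsewhere, when the protocol stops dosing, it keeps the person under observation, even after a serious adverse reaction. Section 9.8.5 is the outlier.

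At stake is long-term safety follow-up in a first-in-human trial. Section 5.8.1 says it is unknown whether the very rare reactions seen with ChAdOx1 nCoV-19 occur with other ChAdOx1 vaccines, and several of them are on the AESI list. A participant with a second adenoviral exposure is someone whose safety one would still want to observe. Staff who work from section 9.8.5 could end that person's follow-up; staff who work from section 9.7 would keep it.

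**Working it through.** **The rules side by side**

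| Section | Trigger | Dosing | Follow-up |
|---|---|---|---|
| 9.8.5 | Any adenoviral vaccine during the trial | Ends, by implication | Ends, if read literally |
| 8.2 item 7 | Same | Ends | Not mentioned |
| 9.7 | Includes ineligibility arising during the study | May be stopped | Continues unless consent is withdrawn |
| 8.3 | Serious adverse reaction, pregnancy | Ends | Continues |
| 11.24.1, 11.24.2 | Holding rules | Held or stopped | Safety follow-up continues, subject to consent |
| 13.1.4 | Early termination of the trial | Ends | Continues for safety |

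**Can section 9.8.5 be read as a dosing rule only?** Before the second injection it can. After it, no trial dose remains. For the 281 nominal days from V2 to the last visit, the sentence either has no effect or ends follow-up.

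**Per-person loss under the literal reading.** Inputs: V2 at nominal D84 (section 4) and the last visit at V2+281 (sections 4 and 6.1). The nominal end is 84 + 281 = D365. Loss = 365 minus the day of the outside vaccine.

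| Outside vaccine given | Study day | Days lost | Share of 365 |
|---|---|---|---|
| D28 | 28 | 337 | 92% |
| V2+14 | 98 | 267 | 73% |
| V2+28 | 112 | 253 | 69% |
| V2+180 | 264 | 101 | 28% |

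These dates are illustrations; the protocol gives no rate or timing for outside adenoviral vaccination. In Cohort 2 the ELISA timepoints are D0, D14, D28, V2, V2+14, V2+28 and V2+281. Leaving after V2+28 therefore loses 1 of 7. Under section 9.7 every loss above is zero.

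**Scale.** One person is 1/20 = 5% of a vaccine group, or 1/46 = 2.2% of vaccine recipients.

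**The protocol's own figure.** Section 13.1.2 gives a probability of more than 90% of seeing at least one participant with an adverse event at a 5% rate among 46 recipients: 1 − 0.95^46 = 0.9055, which agrees. If one person were lost before any event could be seen, 1 − 0.95^45 = 0.9006, still above 90%. With two lost, 1 − 0.95^44 = 0.8953. The figure counts people who received at least one dose. A later exit does not change that count, so the stated figure stands.

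**The case against.** There is a fair case that this is loose wording and not a true conflict. Section 8.2 is silent on follow-up, so both sentences can hold at once: someone who leaves the trial also gets no more doses. Section 9.8.5 speaks of eligibility and never says the person is withdrawn. Section 9.7 names ineligibility arising during the study among the cases where follow-up continues, and the commitment in 11.24.1 and 11.24.2 to follow everyone vaccinated points the same way. That part stands. A reader might infer that the protocol orders withdrawal and so definitely ends SAE collection under section 11.15; the text does not go that far. But section 9.7 is a weak rescue: its paragraph opens with participant safety and is permissive about what may be stopped. Nothing says that it overrides 9.8.5.

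Ending participation after a confounding exposure can also be defended. An adenoviral vaccine within the preceding year is an exclusion criterion, and anti-vector immunity is an exploratory objective. Later AESIs could not be cleanly attributed to the trial vaccine. This too stands, but such data can be flagged, whereas data never collected cannot be recovered.

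Timing is a further limit. Version 4.0 is dated 16 August 2024 and the planned period ends in Q4 2024. If that held, at most 137 days remained to 31 December (15 + 30 + 31 + 30 + 31), so a change at that date could recover only part of the larger losses.

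A reader might also infer that section 11.24.2 ends follow-up, since it allows withdrawal from the study when a temporary exclusion blocks the second dose. The documents do not support this: that wording is discretionary and the next paragraph restores safety follow-up for everyone vaccinated.

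**Conclusion.** The point holds as a wording fault in section 9.8.5 that should be corrected. The sentence departs from how the rest of the protocol treats people whose dosing stops. After the second injection, its only possible effect is to cut short primary outcome (e).

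Its size per person runs from zero, if section 9.7 is applied, to most of the follow-up year under the literal reading (69% at V2+28). These values rest on nominal visit days and chosen dates. The number of people affected is unknown and probably very small. Data collected before exit are kept (sections 9.7 and 13.1.6), and no stated figure changes. The point does not show that any participant's follow-up was or must be ended, nor that the trial's safety conclusions are at risk.

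**What to change.** In section 9.8.5, replace the final clause with: *will not receive further trial vaccinations but will continue scheduled follow-up, including SAE/AESI collection, unless consent is withdrawn*. Leave the investigator's general discretion in section 9.7 as it is. In the analysis, flag data collected after the outside vaccine. Other vaccinations are already reviewed at vaccination and follow-up visits (sections 9.4.1 and 9.4.2).

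Optionally, change the phrase in section 11.24.2 on withdrawal from the study to withdrawal from further vaccination. This is for consistency of wording only.

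The cost is one sentence and an analysis flag; the visits are already scheduled. If the change is judged a substantial amendment it needs approval under section 14.3, so it is best bundled with another. The small downside is that later AESI and immunogenicity results in such a participant are confounded by the outside vaccine, which is why the flag is needed.
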